- If study intervention is permanently discontinued, the participant will be asked to remain in the study after the Follow-up visit without study intervention and continue to comply with study visit schedules for approximately 2 years after the last dose of study intervention or until study end, whichever occurs first; refer to [Section 7.1.1.1](#) for further details.

Data Monitoring Committee: Yes

Statistical Methods

For the primary safety endpoint, there is no formal hypothesis testing. The analyses will be descriptive. Summary statistics for each group with 95% confidence intervals (CIs) will be provided. Estimands are not applicable since there is no formal statistical hypothesis testing for this study.

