9.4.2. Efficacy Analyses

Efficacy data will be summarized by the treatment assignment based on efficacy population. The baseline is defined as the last measurement before the first dose in the placebo-controlled phase.

The secondary endpoints for SALT include both the overall SALT and AA SALT scores. The overall SALT score includes hair loss regardless of etiology (ie, scalp hair loss due to both non-AA and AA). The non-AA SALT score only takes into account scalp hair loss other than that due to AA and is required to be assessed only at:

- Month 9 (end of TP1) (or Month 6 for those participants, who enter the active therapy extension phase at Month 6),
- Month 15E (end of TP2) or Early Termination visit (as appropriate), and
- Month 51E (end of TP3) or Early Termination visit (as appropriate).

The AA SALT score at each visit will be calculated using non-AA SALT scores as follows:

- the non-AA SALT score collected at Month 9 (or Month 6) or the Early Termination visit (as appropriate) will be used for visits in TP1.

- the non-AA SALT score collected at Month 15E or the Early Termination visit (as appropriate) will be used for visits in TP2, and
- the non-AA SALT score collected at Month 51E or the Early Termination visit (as appropriate) will be used for visits in TP3.
- The formula for deriving the AA SALT score is given by: AA SALT score = overall SALT score – non-AA SALT score.

PCD CSR (Month 9; TP1)	
Endpoint	Statistical Analysis Methods
Primary	
 • There are no primary efficacy endpoints.
Secondary	
 • For PGI-C response, for the placebo-controlled phase, number and percentage with 95% confidence interval (based on Clopper-Pearson method) by treatment group, and treatment difference with 95% confidence interval (based on Chan and Zhang's exact method⁽⁵⁶⁾) will be presented. Participants who discontinue from the study for any reason or who switch to active therapy extension phase before Month 9 will be considered as non-responders. • In the placebo-controlled phase, change from baseline in overall and AA SALT score will be analyzed using linear mixed-effects model with baseline, treatment group, visit and treatment group by visit interaction as fixed effects, and participant as a random effect with unstructured covariance matrix assumption. The estimated mean, mean difference, with 95% confidence interval based on the model will be presented at each time point.

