9.4.3. Safety Analyses

The safety analyses will be summarized by initial treatment group in the safety population based on observed data. The baseline is defined as the last measurement before the first dose in the placebo-controlled phase.

All standard safety summary such as the incidence of safety events will be summarized by the initial treatment group for the placebo-control phase, the active therapy extension phase and TP3 extension phase. For initial active group, the overall summary for the whole study duration will also be provided.

PCD CSR (Month 9; TP1)	
Endpoint	Statistical Analysis Methods
Primary	
 The primary endpoint is change from baseline in I-V interwave latency on BAEP at Month 9. It will be analyzed using linear mixed-effects model with baseline, treatment group, visit (Months 6 and 9) and treatment group by visit interaction as fixed effects, and subject as a random effect with unstructured covariance matrix assumption. For participants who switch to the active therapy extension phase at Month 6, only their data through Month 6 will be included in the analysis of the placebo-controlled period. The estimated means, with their standard errors and 95% confidence intervals based on the model will be presented.
Secondary	
 Change from baseline in I-V interwave latency on BAEP during the placebo-controlled phase will be analyzed using linear mixed-effects model with baseline, treatment group, visit (Months 6 and 9) and treatment group by visit interaction as fixed effects, and participant as a random effect with unstructured covariance matrix assumption. The estimated means, with their standard errors and 95% confidence intervals based on the model will be presented. For data in the active therapy extension phase, descriptive statistics will be presented. For change from baseline in IENFD at Month 9 and Month 15E and change from baseline in axonal dystrophy in skin punch biopsies at Month 9 and Month 15E: descriptive statistics will be presented. Change and percent change from baseline in amplitude of wave V: the same method linear mixed-effect model as

PCD CSR (Month 9; TP1)	
Endpoint	Statistical Analysis Methods

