##### 5.1. Hypotheses and Decision Rules

For the primary safety endpoint, there is no formal hypothesis testing. The analyses will focus on estimation. Summary statistics for each group with 95% confidence intervals will be provided.

No estimands will be defined since there is no formal statistical hypothesis testing for this study.

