## 6. ANALYSES AND SUMMARIES

### 6.1. Primary Endpoint

- Primary endpoint: Change from baseline in I-V interwave latency on BAEP at a stimulus intensity of 80 decibels (dB) at Month 9;
- Population: Safety;
- Statistical Method: a linear mixed-effects model in Section 5.2, which includes all the post-baseline measurements through Month 9, will be used. The estimated means, with standard errors and 95% confidence intervals for each treatment group based on the model will be presented. Descriptive statistics will also be provided based on the observed data. Data from right side and left side will be summarized separately.

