### **6.2.4. Amplitude of Wave V on BAEP**

- Endpoint: Change and percent change from baseline in amplitude of wave V on BAEP at a stimulus intensity of 80dB at Months 6, 9, 9E, and 15E.
- Population: Safety.

- **Statistical Method:** For change from baseline, a linear mixed-effects model for Months 6 and 9 in [Section 5.2](#) will be used. The estimated means, with standard errors and 95% confidence intervals for each treatment group based on the model will be presented. Descriptive statistics based on observed data will also be provided. Descriptive statistics will be presented for data in the active therapy extension phase. Data from right side and left side will be summarized separately. For percent change from baseline, descriptive statistics will be presented.

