### **6.3. Secondary and exploratory Endpoints-Efficacy**

#### **6.3.1. Overall and AA SALT Scores**

- Endpoint: Change from baseline in overall and AA SALT scores in all the timepoints collected.

The AA SALT score at each visit will be calculated using non-AA SALT scores as follows:

- the non-AA SALT score collected at Month 9 (or Month 6) or the Early Termination visit (as appropriate) will be used for visits in TP1.
  - the non-AA SALT score collected at Month 15E or the Early Termination visit (as appropriate) will be used for visits in TP2, and
  - the non-AA SALT score collected at Month 51E or the Early Termination visit (as appropriate) will be used for visits in TP3.
  - The formula for deriving the AA SALT score is given by: AA SALT score = overall SALT score - non-AA SALT score.
  - non-AA scores that were blank will be considered as zero in cases there was no medical history indicating AGA
- Population: Efficacy.
  - Statistical Method: For placebo-controlled phase, a linear mixed-effects model in [Section 5.2](#) will be used. The estimated mean, standard errors and 95% confidence intervals for each treatment group, and mean difference with 95% confidence interval will be presented at each time point. Descriptive statistics will be presented for data in TP2 and TP3.

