### **6.3.2. PGI-C Response**

- Summary: Proportion of subjects with PGI-C response defined as greatly improved or moderately improved at all the timepoints collected.
- Population: Efficacy.
- Statistical Method: For placebo-controlled phase, statistics including number and percentage with 95% confidence interval (based on Clopper-Pearson method) by treatment group, and treatment difference with 95% confidence interval (based on Chan and Zhang's exact method) will be presented. Missing data will be treated as non-responders. Summary based on observed data will also be provided. For TP2 and TP3, descriptive statistics including number and percentage with 95% confidence interval (based on Clopper-Pearson method) will be presented based on observed data.

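### The placebo-controlled analyses of I-V latency (primary) and wave V amplitude report each arm's model mean but no ritlecitinib-minus-placebo difference with a confidence interval; adding one is an inexpensive improvement

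*SAP*

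**What the plan says.** SAP 5.2 defines one linear mixed-effects specification for the placebo-controlled period, covering latency, wave V amplitude and SALT. Its fixed effects are baseline, treatment, visit and treatment by visit. The planned outputs then differ by endpoint.

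- **Latency and wave V amplitude.** SAP 6.1 gives: "The estimated means, with standard errors and 95% confidence intervals for each treatment group based on the model will be presented". SAP 6.2.1 and 6.2.4 repeat this for Month 6 latency and for amplitude, where the method is "a linear mixed-effects model for Months 6 and 9 in" SAP 5.2. Protocol 9.4.3 gives: "The estimated means, with their standard errors and 95% confidence intervals based on the model will be presented", and applies the same method to amplitude. No between-arm difference is named.
- **SALT.** Protocol 9.4.2 gives: "The estimated mean, mean difference, with 95% confidence interval based on the model will be presented at each time point". SAP 6.3.1 likewise lists per-arm means "and mean difference with 95% confidence interval will be presented at each time point".
- **PGI-C.** SAP 6.3.2 gives per-arm percentages "and treatment difference with 95% confidence interval".

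The stated stance is per-group estimation without testing. SAP 5.1 says: "The analyses will focus on estimation. Summary statistics for each group with 95% confidence intervals will be provided". The protocol synopsis says of the primary endpoint: "The analyses will be descriptive". The sample-size sections give a 95% half-width of 0.07 ms for one group of 30, assuming an SD of 0.2 ms.

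**The concern.** The trial is randomised 1:1 against placebo. Protocol 4.2 explains that the 9-month placebo-controlled phase is there to evaluate the drug's effect over the period in which the dog findings appeared. That effect is ritlecitinib minus placebo. A within-arm change also carries retest and equipment drift, which the placebo arm allows one to subtract.

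As planned, two secondary efficacy endpoints come with a treatment-effect estimate and interval, and the primary safety endpoint does not. The lack of a hypothesis test does not explain this, because SAP 7 says no hypotheses are tested anywhere in the study.

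Two things are at stake. A reader may judge the arms by whether their separate intervals overlap, which is a blunter comparison than an interval for the difference. A reader may also carry the per-group 0.07 ms over to the comparison, where it is too small.

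**Working it through.** **Inputs.** From the sample-size sections (Protocol 9.2; SAP, Sample Size Determination): SD of change 0.2 ms, published SD range 0.1 to 0.3 ms, 30 per arm. All figures are half-widths of 95% intervals.

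**1. The plan's own figure.** The formula is 1.96 × SD/√n. Here 0.2/√30 = 0.0365, and 1.96 × 0.0365 = 0.0716 ms. With t on 29 df it is 0.0747 ms. Both round to the stated 0.07, which is correct for a single group.

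**2. Difference between arms, unadjusted.** SE = SD × √(2/n) = 0.2 × √(2/30) = 0.0516.

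| SD (ms) | z | t, 58 df |
|---|---|---|
| 0.1 | 0.0506 | 0.0517 |
| 0.2 | 0.1012 | 0.1034 |
| 0.3 | 0.1518 | 0.1551 |

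At SD 0.2, 0.1012/0.0716 = 1.41, the square root of 2.

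**3. Difference between arms, adjusted for baseline.** The planned model includes baseline, so the residual SD matters. The documents give no baseline/follow-up correlation ρ, so it is assumed, with equal variances at the two times. Holding the SD of change at 0.2, the score SD is 0.2/√(2(1−ρ)) and the residual SD is the score SD × √(1−ρ²). The half-width is t(57 df) × residual SD × √(2/30).

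| ρ (assumed) | Half-width (ms) | Ratio to 0.0716 |
|---|---|---|
| 0.3 | 0.0834 | 1.16 |
| 0.5 | 0.0896 | 1.25 |
| 0.7 | 0.0953 | 1.33 |
| 0.8 | 0.0981 | 1.37 |

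The row for 0.5 is closest to the plan. With equal variances, an SD of change equal to the SD of the score requires 2(1−ρ) = 1, so ρ = 0.5.

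**4. Overlap compared with a difference interval.** At SD 0.2 and n = 30, unadjusted, the two per-arm intervals stop overlapping when the means differ by 2 × 0.0716 = 0.143 ms (z) or 2 × 0.0747 = 0.149 ms (t). An interval for the difference excludes zero from 0.101 ms (z) or 0.103 ms (t).

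**5. Recoverability.** The arms are separate participants, so √(SE₁² + SE₂²) should be close to the model's SE of the difference. In 20,000 simulated baseline-adjusted single-visit datasets with 30 per arm, it was 99.8% of that SE (median; 95% range 97.9% to 100%).

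**The case against.** The strongest reply is that this is a declared choice, applied consistently. The synopsis, Protocol 9.1, SAP 5.1, the endpoint sections and the precision statement all speak per group. The primary objective speaks of assessing latency in treated participants and contains no comparative wording. Differences are planned only for efficacy, on a different analysis set. All of this stands, and it rules out calling the omission a contradiction or an error.

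Four stronger readings are tempting, and the documents do not support them.

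- **That the comparison is lost.** It is not; step 5 shows it can be closely rebuilt from the planned output.
- **That 0.07 ms is wrong, or that the plan applies it to the comparison.** It reproduces, and both sample-size sections label it as a group figure.
- **That the comparison is always 1.4 times less precise than stated.** That ratio sets one unadjusted figure against another. Against the stated per-group figure, the baseline-adjusted difference is about 1.2 to 1.4 times as wide.
- **That participants who leave early contribute nothing at Month 9, so a smaller sample should be assumed.** BAEP is done at early termination, and SAP Appendix 1 assigns Days 227 to 316 to Month 9, up to the start of active extension treatment, so some of those recordings can count. Month 6 values also stay in the mixed model and inform the Month 9 estimate. In the other direction, Protocol 4.1 allows up to 20 more participants; 40 per arm would give 0.089 ms unadjusted at SD 0.2.

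Timing also counts against urgency. The SAP version history shows that analyses had already been added to the primary-completion report by version 4.0, so the row would probably not be prespecified there.

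**Conclusion.** The point holds as an inexpensive improvement to a coherent plan. For change in I-V latency (Months 6 and 9) and wave V amplitude (Months 6 and 9), no between-arm difference with an interval is planned, although SALT from the same model specification and PGI-C both get one.

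For latency, the between-arm half-width is about 0.10 ms unadjusted at SD 0.2 with 30 evaluable per arm, and 0.05 to 0.16 ms over the documents' SD range. With baseline adjustment it is about 0.08 to 0.10 ms at SD of change 0.2. The adjusted figures rest on assumed correlations of 0.3 to 0.8 and equal variances. All are single-visit approximations for one ear and ignore missing data. The documents give no precision inputs for amplitude, so no size is attached to it.

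Absence of wave V is outside this point, since SAP 6.2.5 gives it counts and percentages only.

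**What to change.** In SAP 6.1, 6.2.1 and 6.2.4 and Protocol 9.4.3, add the least-squares mean difference (ritlecitinib minus placebo) with SE and 95% interval at Months 6 and 9, separately by ear, from the existing SAP 5.2 model. No test and no alpha are needed. If the primary-completion report is already complete, label the row post hoc.

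In the sample-size sections, keep 0.07 ms, described explicitly as the unadjusted per-group half-width. Add the between-arm half-widths given in the verdict, with their assumptions.

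The cost is a few output rows and some wording. The treatment-by-visit term is already in the model and no new data are required. The stated precision for the comparison will look less favourable than 0.07 ms.

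A separate minor alignment point: SAP 6.2.1 fits the Month 6 latency model to data through Month 6 only, whereas Protocol 9.4.3 names a single model with Months 6 and 9. The two should be reconciled on their own account.

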## Sample Size Determination

Approximately 60 adults 18 to 50 years of age will be randomized in a 1:1 allocation ratio to either the PF-06651600 200 mg QD/50 mg QD dose group or the placebo group.

For the primary safety endpoint, change from baseline in I-V interwave latency on BAEP at Month 9, the published standard deviations for I-V interwave latency on BAEP range from 0.1 to 0.3 ms. Assuming a standard deviation of 0.2 ms, and assuming the standard deviation of change from baseline is similar to the standard deviation of actual score, the half-width of 95% confidence interval for the group will be 0.07 ms for 30 participants per group.

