## 3. ENDPOINTS AND BASELINE VARIABLES: DEFINITIONS AND CONVENTIONS

### 3.1. Primary Endpoint – Safety in TP1

- Change from baseline in I-V interwave latency on BAEP at a stimulus intensity of 80 decibels (dB) at Month 9.

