##### 5.2. General Methods

In the placebo-controlled period, the following continuous endpoints: (change from baseline in I-V interwave latency on BAEP, change from baseline in amplitude of wave V, and change from baseline in overall and AA SALT score, will be analyzed using the linear mixed -effects model with baseline, treatment group, visit, and treatment group by visit interaction as fixed effects, with an unstructured covariance matrix assumption, if there are convergence issues, a compound symmetry matrix will be used. The Kenward-Roger degrees of freedom approximation will be used. For participants who switch to the active therapy extension phase at Month 6, only their data through Month 6 will be included in the analysis of the placebo-controlled period. Descriptive statistics based on observed data will also be provided. For TP2 and TP3, descriptive statistics will be presented.

For the binary endpoint PGI-C response, in the placebo-controlled phase, number and percentage of responders with 95% confidence interval (based on Clopper-Pearson method) by treatment group, and treatment difference with 95% confidence intervals (based on Chan and Zhang's exact method) will be presented. Participants who discontinue from the study for any reason or who switch to active therapy extension phase before Month 9 will be considered as non-responders. Number and percentage based on observed data will also be provided. For TP2 and TP3, number and percentage of responders with 95% confidence interval (based on Clopper-Pearson method) will be presented based on observed data.

For all other data, descriptive summary statistics such as number and percentage will be presented for binary variables, and number, mean, standard deviation (or standard error of the mean), median, minimum, and maximum will be presented for continuous variables.

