## 7. INTERIM ANALYSES

There is no formal interim analysis planned in this study. However, if required, interim analyses may be performed for study monitoring for internal decision making, due to regulatory requests, or to support regulatory submissions. As no statistical hypotheses will be tested in this study, there are no issues of protecting the Type I error rate.

This study uses an External Data Monitoring Committee (E-DMC). The E-DMC will be responsible for ongoing monitoring of safety of subjects in the study according to the DMC charter. The recommendations made by DMC to alter the conduct of the study will be forwarded to the appropriate Pfizer personnel for final decision. Pfizer will forward such decisions, which may include summaries of aggregate analyses of safety data, to regulatory authorities, as appropriate.

Independent safety adjudication committees will be used for opportunistic infections, cardiovascular events, neurological, including audiological events, and malignancy events.

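### The single primary endpoint is reported separately for right and left ears, with no participant-level estimate, so each group has two estimates for one question about a central effect

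*SAP*

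**What the plan says.** Both documents name one primary endpoint. SAP Section 3.1 gives it as "Change from baseline in I-V interwave latency on BAEP at a stimulus intensity of 80 decibels (dB) at Month 9", and Protocol Section 9.4.3 agrees: "The primary endpoint is change from baseline in I-V interwave latency on BAEP at Month 9". Neither says which ear, or what combination of ears, is meant.

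The precision statement is also a single figure. SAP Sample Size Determination says "the half-width of 95% confidence interval for the group will be 0.07 ms for 30 participants per group", and Protocol Section 9.2 gives the same value.

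The model in SAP Section 5.2 has "baseline, treatment group, visit, and treatment group by visit interaction as fixed effects, with an unstructured covariance matrix assumption". Section 6.1 applies it to the primary endpoint and specifies the output: "The estimated means, with standard errors and 95% confidence intervals for each treatment group based on the model will be presented". It adds descriptive statistics on observed data and closes with "Data from right side and left side will be summarized separately". The same closing instruction appears for the other BAEP endpoints in SAP Sections 6.2.1, 6.2.4 and 6.2.5. The protocol's account of the primary analysis does not mention side.

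The stated aim is estimation. SAP Section 5.1 says "For the primary safety endpoint, there is no formal hypothesis testing. The analyses will focus on estimation".

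**The concern.** The endpoint and the precision statement both imply one value per participant, but each participant contributes two ears. Neither document defines a two-ear mean, a worse-ear value, a designated primary ear, or a way to read the ears together when they disagree. If one ear shows a shift and the other does not, the plan does not say which estimate answers the primary objective.

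By the protocol's own rationale, the question concerns the participant rather than the ear. Section 4.2 chose I-V latency because the dog finding was judged central. Section 2.2.1 describes the first dog study's brainstem lesion as bilateral, and the auditory deficits in the second as central rather than peripheral. The drug is oral. Each ear is therefore a measurement of the same brainstem, and a central effect would be expected in both.

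There is also a practical matter. Protocol Section 8.2.7 admits only centrally confirmed BAEP results to the analysis. A participant may have one usable ear, so the right and left results may rest on different sets of participants.

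**Working it through.** **Inputs.** SD 0.2 ms, published SD range 0.1 to 0.3 ms, n = 30 per group and 95% confidence, all from SAP Sample Size Determination. The correlation r between the two ears' change scores is in neither document. It is an assumption, varied here from 0 to 1.

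**Step 1: reproduce the plan's figure.** Half-width for one group mean = z × SD/√n = 1.960 × 0.2/√30 = 0.0716 ms. With the t quantile on 29 degrees of freedom it is 0.0747 ms. Both round to the stated 0.07 ms. The formula uses one value per participant, so it describes a single-ear analysis if 0.2 ms is a per-ear SD. The documents do not say whether it is.

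**Step 2: combine the ears.** With equal SD in each ear and both ears observed, the SD of a participant's two-ear mean is SD × √((1+r)/2). The half-width is then 1.960 × 0.2 × √((1+r)/2)/√30, and the equivalent number of single-ear participants is 2 × 30/(1+r).

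| r (assumed) | SD of mean (ms) | Half-width (ms) | Narrower than one ear | Equivalent n per group |
|---|---|---|---|---|
| 0 | 0.141 | 0.051 | 29% | 60 |
| 0.3 | 0.161 | 0.058 | 19% | 46 |
| 0.5 | 0.173 | 0.062 | 13% | 40 |
| 0.7 | 0.184 | 0.066 | 8% | 35 |
| 0.8 | 0.190 | 0.068 | 5% | 33 |
| 0.9 | 0.195 | 0.070 | 2.5% | 32 |
| 1 | 0.200 | 0.072 | 0% | 30 |

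Like the plan's own figure, this ignores any gain from baseline adjustment or the Month 6 data.

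**Step 3: information kept by one ear.** This is 30 divided by the equivalent n: 30/60 = 50% at r = 0, 30/40 = 75% at r = 0.5, and 30/33.3 = 90% at r = 0.8.

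**Step 4: joint coverage of the two intervals.** For one group, the chance that at least one of two 95% intervals misses its true value is 1 − 0.95² = 9.75% at r = 0. From the bivariate normal it is 9.1% at r = 0.5 and 7.8% at r = 0.8. It is 5% at r = 1.

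**Step 5: comparison with uncertainty in the SD.** Over the published SD range, the single-ear half-width runs from 1.960 × 0.1/√30 = 0.036 ms to 1.960 × 0.3/√30 = 0.107 ms. The gain from combining ears is small beside this.

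**The case against.** The strongest case for leaving the plan alone is that separate reporting is pre-specified, used consistently across the BAEP endpoints, and defensible when looking for harm, because averaging can dilute a one-sided change. With both sides always shown, neither can be suppressed. There is no margin or decision rule, and a bilateral effect should appear in both tables. This supports keeping the per-ear results. It does not supply the missing participant-level quantity.

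A second objection is that the separate-sides instruction says summarized and follows the sentence on descriptive statistics, so it may govern only the descriptive tables. That is possible. But SAP Section 5.2 would then leave open how two values per participant per visit enter a model with no ear term. Text is needed on either reading.

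A third is timing. The version history in SAP Section 1 (version 4.0) refers to analyses already added to the PCD-CSR, which carries the primary analysis (SAP Section 8.1). Protocol Section 6.3.1 has sponsor staff unblinded for that report. Both documents also commit to a protocol amendment for major changes to the primary endpoint or its analysis. This stands: a combined estimate should be added and labelled, not substituted for the planned results.

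A reader might infer three stronger things, none of which the documents support:
- **Each per-ear analysis wastes half the data.** Both ears are reported, each analysis can use every participant with a confirmed result for that ear, and half the information is lost only at r = 0.
- **Two primary estimates inflate type I error.** No test is planned, and SAP Section 7 says "As no statistical hypotheses will be tested in this study, there are no issues of protecting the Type I error rate". Step 4 concerns joint coverage only.
- **The 0.07 ms statement is wrong.** It reproduces for one value per participant.

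**Conclusion.** The point holds as a cheap improvement. The plan poses one primary question about a central effect and sets out two estimates per group to answer it, with nothing at participant level. The main gain from combining the ears is a single, defined answer.

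The gain in precision is secondary. The half-width moves from 0.072 ms to somewhere between 0.051 ms (r = 0) and 0.072 ms (r = 1), with 0.062 ms at r = 0.5 and 0.068 ms at r = 0.8. These figures assume a per-ear SD of 0.2 ms, equal in the two ears, both ears observed, 30 participants per group and a non-negative r. The documents do not give r, so no single figure can be claimed.

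**What to change.** Add to SAP Section 6.1 one combined estimate for each group at Month 9, from the Section 5.2 model extended with ear as a repeated within-participant factor and a between-ear covariance, and report the mean over ears with its standard error and 95% interval. This form keeps participants with only one centrally confirmed ear, which a simple two-ear average would not without a further rule.

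State the covariance structure explicitly. Two ears at two visits give four measurements, so a fully unstructured matrix has 4 × 5/2 = 10 parameters, and the compound-symmetry fallback in Section 5.2 should say how it treats ear and visit.

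Keep the right and left results as supportive, say whether the separate-sides instruction applies to the model or only to the descriptive tables, and say whether the 0.2 ms SD is per ear. If the Month 9 analysis has already been reported, label the combined estimate post hoc or supplementary.

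The cost is a few sentences and one more model fit, with no new data or visits. The small downside is that a one-sided effect is diluted in the combined estimate; the retained per-ear results would show it.
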